6.4 STATISTICAL ANALYSIS

6.4.1 Analysis Variables

The analysis variables consist of baseline variables, pharmacokinetics and safety variables for primary and secondary objective analyses.

6.4.2 Baseline Demographics

Baseline characteristics including demographics and laboratory measurements will be summarized using descriptive statistics.

6.4.3 Safety Analysis

Summaries of the number and percentage of subjects experiencing any AE or reactogenicity will be tallied by subgroup, and presented along with exact 95% confidence intervals for the proportion.

Solicited AEs: Solicited AE data is collected after each dose administered in this study. The number and percentage of subjects experiencing each type of solicited sign or symptom will be tabulated by severity. For a given sign or symptom, each subject's solicited AEs will be counted once under the maximum severity for all assessments.

Unsolicited AEs: Unsolicited AEs are coded into MedDRA preferred terms. The number and percentages of participants experiencing each specific AE will be tabulated by severity and relationship to treatment. For the calculations in these tables, each participant's adverse experience will be counted once under the maximum severity or strongest recorded causal relationship to treatment.

A complete listing of adverse experiences for each participant will provide details including severity, relationship to treatment type, onset, duration and outcome.

Local Laboratory Values: Boxplots of local laboratory values will be generated for baseline values and for values measured during the course of the study. Each boxplot will show the 1st quartile, the median, and the 3rd quartile. Outliers, or values outside the boxplot, will also be plotted. If appropriate, horizontal lines representing boundaries for abnormal values will be plotted.

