3. STUDY OBJECTIVES

3.1 PRIMARY OBJECTIVES

- To evaluate the safety and tolerability of VRC-HIVMAB075-00-AB administered as a single dose at 1 mg/kg IV, 5 mg/kg IV, 20 mg/kg IV, 40 mg/kg IV, and 5 mg/kg SC to healthy adults.
- To evaluate the safety and tolerability of VRC-HIVMAB075-00-AB administered at 20 mg/kg IV by repeat dosing every 12 weeks for a total of 3 infusions to healthy adults.
- To evaluate the safety and tolerability of VRC-HIVMAB075-00-AB administered at 5 mg/kg SC by repeat dosing every 12 weeks for a total of 3 injections to healthy adults.

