4.3 CRITERIA FOR DOSE AND ROUTE ESCALATION

There are three dose escalation reviews in this study and one route escalation review. The Protocol Safety Review Team (PSRT, Section 8.9) will conduct an interim safety data review before dose escalation and repeat dosing may occur. The PSRT must assess the data as showing no significant safety concerns before proceeding with enrollment of the next groups.

- The first dose escalation review (from 1 mg/kg IV to 5 mg/kg IV) will occur when at least 3 subjects who received the 1 mg/kg IV dose have completed 2 weeks of safety follow-up visits. The PSRT review will determine if enrollments in Group 2 may begin.
- The only route escalation review and the second dose escalation review (from 5 mg/kg IV to 5 mg/kg SC and 20 mg/kg IV, respectively) will occur when at least 3 subjects who received the 5 mg/kg IV dose have completed 2 weeks of safety follow-up visits. The PSRT review will determine if enrollments in Group 3 (5 mg/kg SC), Group 6 (5 mg/kg SC by repeat dosing), Group 4 (20 mg/kg IV) and Group 7 (20 mg/kg IV by repeat dosing) may begin.
- The third dose escalation review (from 20 mg/kg IV to 40 mg/kg IV) will occur when at least 3 subjects who received the 20 mg/kg IV dose have completed 2 weeks of safety follow-up visits. This review will determine if enrollments in Group 5 (40 mg/kg IV) may begin.
- Additionally, the second and third doses can be administered in Groups 6 and 7 once the initial dose is assessed as safe for further evaluation.

If the first product administration is not completed or there are discontinuations from the study before there are sufficient data to conduct the dose escalation review for a group, then extra subjects may be enrolled into that group in order to have the requisite data on at least 3 subjects.

Additionally, AEs assessed as related to the study product at the time of a dose escalation review may be judged by the PSRT to warrant adding additional subjects at a given dose group.

The IRB will be provided with documentation of the safety review process and notification of the dose escalation. Consultation with the IRB and FDA, if needed, as per study pause criteria (Section 4.5) will occur if indicated by the review. One outcome of a dose escalation review may be to recommend evaluation of additional subjects at the current dose and reassess for safety before proceeding to a higher dose.

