6.3.1 Treatment Assignments

In this dose-escalation study, subjects will be assigned to the dose group that is open to accrual at the time of enrollment.

When a subject is enrolled into a group but does not begin product administrations, a new eligible subject may be enrolled into the same group. If any replacement is needed in case of subject withdrawal, the replacement subject will be assigned to the same treatment as the dropout subject in order to complete the safety dataset as planned.

Dose escalation rules are described in Section 4.3.

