6.3.2 Sample Size Considerations

This study is primarily descriptive. For safety analysis, the goal is to identify safety concerns associated with different VRC07-523LS doses. There may be as few as 3 to 5 subjects in a group at the time of a dose escalation; therefore, this section considers group sizes of both n=3 and n=5.

The ability to identify serious adverse experiences is best expressed by the maximum true rate of SAE that would unlikely be observed and the minimum true SAE rate that would very likely be observed. Within a group of size n=3, there is a 90% chance of observing at least 1 event if the true rate is no less than 0.536 and a 90% chance of observing no event if the true rate is no bigger than 0.034. Within a group of size n=5, there is a 90% chance of observing at least 1 event if the true rate is no less than 0.37 and a 90% chance of observing no event if the true rate is no bigger than 0.02.

Probabilities of observing 0 or more than 1 event are presented in Table 4 for a range of possible true event rates. These calculations provide a complete picture of the sensitivity of this study design to identify potential safety problems with the study product. For example, within the group of size n=3, if the true event rate is 0.01, then there is a probability of 0.97 to observe no event and a probability of <0.001 to observe more than 1 event; while, within the group of size n=5, if the true event rate is 0.01, then there is a probability of 0.951 to observe no event and a probability of 0.001 to observe more than 1 event.

Table 4: Probability of Event for Different Scenarios

True event rate	Within a group (n=3)		Within a group (n=5)	
	Pr(0 event observed)	Pr(more than 1 event observed)	Pr(0 event observed)	Pr(more than 1 event observed)
0.01	0.97	0	0.951	0.001
0.03	0.913	0.003	0.859	0.008
0.05	0.857	0.007	0.774	0.023
0.1	0.729	0.028	0.59	0.081
0.2	0.512	0.104	0.328	0.263
0.3	0.343	0.216	0.168	0.472
0.4	0.216	0.352	0.078	0.663

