6.4.4 Tolerability Evaluation

The tolerability of the medical product represents the degree to which overt adverse effects can be tolerated by the subject [19]. VRC 605 is the first trial of VRC07-523LS in healthy adults. The tolerability evaluation will be mostly descriptive by nature and consist of solicited AEs that occur during the 3 days following each VRC07-523LS administration and reasons for any withdrawal or discontinuation based upon subject discomfort. This early assessment of tolerability of VRC07-523LS will inform which parameters should be solicited or routinely assessed to further characterize the tolerability profile in a larger number of subjects.

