7.5 RISKS

Risks of Administration of MAbs: Administration of MAbs may have a risk of immune reactions such as acute anaphylaxis, serum sickness and the generation of antibodies. However, these reactions are rare and more often associated with MAbs targeted to human proteins or with the use of murine MAbs that would have a risk of human anti-mouse antibodies [20]. In this regard, because VRC07-523LS is targeted to a viral antigen and is a human MAb, it is expected to have a low risk of such side effects.

Typically, the side effects of MAbs are mild and may include reactions at injection site (pain, redness, bruising swelling), fever, chills, rigors, nausea, vomiting, pain, headache, dizziness, shortness of breath, bronchospasm, hypotension, hypertension, pruritus, rash, urticaria, angioedema, diarrhea, tachycardia or chest pain. Clinical use of MAbs that are targeted to cytokines or antigens associated with human cells may be associated with an increased risk of infections [20]; however, this is not expected to be a risk for a MAb targeted to a viral antigen.

It is known from published experience with human MAbs directed against the cell surface targets on lymphocytes that infusion of a MAb may be associated with cytokine release, causing a reaction known as “cytokine release syndrome” (CRS) [21]. Most infusion-related events occur within the first 24 hours after beginning administration. Severe reactions, such as anaphylaxis, angioedema, bronchospasm, hypotension and hypoxia, are infrequent and more often associated with MAbs targeted to human proteins or with non-human MAb, such as a murine MAb [20]. CRS reactions most commonly occur within the first few hours of beginning infusion and with the first MAb infusion received. This is because the cytokine release is associated with lysis of the cells targeted by the MAb and the burden of target cells is greatest at the time of the first MAb treatment. With licensed therapeutic MAbs, CRS is managed by temporarily stopping the infusion, administering histamine blockers and restarting the infusion at a slower rate [22].

Delayed allergic reactions to a MAb may include a serum sickness type of reaction, which is characterized by urticaria, fever, lymph node enlargement, and joint pains. Symptoms may not appear until several days after the exposure to the Mab. This type of reaction is noted to be more common with chimeric types of MAb [20].

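### Section 6.4.3 could add pooled first-dose safety summaries for Groups 3+6 and 4+7 and by-dose rows for Groups 6 and 7: an improvement, not an error

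*Combined protocol and SAP*

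**What the plan says.** Section 6.4.3 of the combined protocol and SAP tallies subjects with any AE or reactogenicity by *subgroup*, with exact 95% confidence intervals, and does not define that term. Solicited data are collected after every dose. For a given symptom, however, each subject's "solicited AEs will be counted once under the maximum severity for all assessments". Unsolicited AEs are likewise counted once per participant, at maximum severity or strongest causal relationship. The same section adds: "A complete listing of adverse experiences for each participant will provide details including severity", together with onset and other details.

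Section 3.1 makes both kinds of exposure primary. One objective covers single doses at five dose and route combinations. The other two cover three doses of 20 mg/kg IV, and 5 mg/kg SC "by repeat dosing every 12 weeks for a total of 3 injections to healthy adults". Section 6.3.2 says that for safety "the goal is to identify safety concerns associated with different VRC07-523LS doses". Section 6.4.4 bases tolerability on "solicited AEs that occur during the 3 days following each VRC07-523LS administration" and on withdrawals for discomfort. Under Section 4.3, doses 2 and 3 may be given "once the initial dose is assessed as safe for further evaluation".

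Table 3 plans 3 subjects in each of Groups 1-5 and 5 in each of Groups 6 and 7. Groups 3 and 6 both start with 5 mg/kg SC, and Groups 4 and 7 both start with 20 mg/kg IV. Section 6.4.5 compares first and last doses in Groups 6 and 7, but for pharmacokinetics only.

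**The concern.** Two useful summaries are not specified.

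- **Pooled first doses.** Until a second dose is given, Group 6 subjects have had the same exposure as Group 3 subjects, and Group 7 the same as Group 4. Section 4.3 opens all four groups after the same review. If the tables follow the group structure only, the single-dose objective at these two regimens is reported from 3 subjects when 8 have had the exposure.
- **Rows by dose number.** One worst-grade count over three doses cannot show whether reactions came with the first dose or on re-exposure. Two of the three primary objectives concern repeat dosing, and the data are gathered dose by dose.

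What is at stake is the precision and clarity of the final safety tables.

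**Working it through.** **Inputs.** Group sizes 3 and 5 (Section 6.3, Table 3). Zero-event bounds 0.708 and 0.522 (Table 5). 90%-detection rates 0.536 and 0.37 (Section 6.3.2). AE reporting for 56 days after each dose (Section 5.1). Dosing on days 0, 84 and 168 with ±7-day windows (Appendix III, Schedules 3 and 4).

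**Step 1: reproduce the plan's figures, then apply them to n = 3 + 5 = 8.**

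- Exact two-sided 95% upper bound with zero events: 1 − 0.025^(1/n).
- True rate with a 90% chance of at least one event: 1 − 0.1^(1/n).
- Chance of at least one event at an assumed true rate of 0.10: 1 − 0.9^n.

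| n | Upper bound, 0 events | 90%-detection rate | Pr(at least 1 event), rate 0.10 |
|---|---|---|---|
| 3 | 0.708 | 0.536 | 0.271 |
| 5 | 0.522 | 0.369 (printed 0.37) | 0.410 |
| 8 | 0.369 | 0.250 | 0.570 |

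The bounds and detection rates at n=3 and n=5 agree with the plan. The n=8 row is new and adds no subject.

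**Step 2: can events be assigned to a dose?** With windows kept, dose 2 falls no earlier than day 84 − 7 = 77. The shortest gap from dose 2 to dose 3 is (168 − 7) − (84 + 7) = 70 days. Both exceed 56, so the AE reporting periods do not overlap.

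**Step 3: what the any-dose row leaves out.** A result of 2/5 (95% CI 0.053 to 0.853, Table 5) is the same whether the numbers reacting at doses 1, 2 and 3 were 2-0-0, 0-0-2 or 2-2-2. This shows what the summary collapses. It does not show that the summary is biased.

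**Step 4: limit of by-dose rows.** If all 5 subjects reacted after dose 3 and none after dose 1, the exact paired two-sided p-value would be 2 × 0.5^5 = 0.0625. Rows at n=5 cannot establish a change between doses.

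**Step 5: denominators.** Section 6.3.1 provides that after a withdrawal "the replacement subject will be assigned to the same treatment as the dropout subject". More subjects may therefore receive dose 1 than dose 3. As an assumed example, if one repeat-dose subject leaves after dose 1 and is replaced, the denominators by dose are 6, 5 and 5. The pooled first-dose n is then 9, with a zero-event bound of 0.336.

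**Step 6: timepoints for local reactions.** By the day headings of Schedule 3, Group 6 has the following after all three doses: day of dosing, 72 h (D3, D87, D171), and weeks 1, 2, 4 and 8. By Schedule 4, Group 7 has day of dosing and weeks 1, 2, 4 and 8 after all three. Its 72 h visit follows doses 2 and 3 only.

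**The case against.** The strongest reply is that nothing is broken. The study is described as primarily descriptive, no between-group test is planned, and the worst-grade count is a standard summary. The participant listing gives onset, so with five subjects the dose can be read by hand. Section 4.3 already sets the 40 mg/kg review by dose received, the safety team reviews data weekly (Section 7.12), and Section 1.3.3 records that the final escalation review has taken place. All of this stands and limits the point to the final tables. It does not remove it, because a listing gives no counts, denominators or intervals by dose.

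Three stronger readings are tempting and are not supported.

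- A reader might infer that the any-dose row is inflated against the single-dose groups. The size is unknown. For an assumed per-dose rate of 0.10, the any-dose rate is 0.10 if the same subjects always react and 1 − 0.9³ = 0.271 if doses are independent. The plan makes no such comparison. This is a reason not to read the rows side by side, and it is not evidence of bias.
- A reader might cite Section 7.5: "CRS reactions most commonly occur within the first few hours of beginning infusion and with the first MAb infusion received". That text concerns antibodies against lymphocyte surface targets and explains the pattern by lysis of target cells. This product targets a viral antigen and is given to HIV-negative adults, so the statement does not support by-dose rows here.
- A reader might infer that the plan rules these summaries out. Because the subgroup is undefined, they are neither excluded nor promised.

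**Conclusion.** The point holds as a low-cost improvement. The pooled first-dose summary is the stronger half: it lowers the zero-event upper bound to 0.369 and the 90%-detection rate to 0.250 for two of the five single-dose regimens. Even so, 0/8 leaves a true rate of up to about 37% compatible with the data. The by-dose rows answer a descriptive question that the any-dose row cannot.

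The n=8 figures assume planned enrollment, with every subject dosed and no replacement. Pooling also assumes that subjects in the two groups of a pair can be treated alike up to the second dose. Same-dose, same-route first exposures opened by one review make that reasonable. No stated figure, sample size or safety-review decision changes.

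**What to change.** In Section 6.4.3:

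1. Add first-dose summaries for Groups 3+6 and Groups 4+7 (planned n=8 each) with exact 95% intervals, using events before any second dose. Use common windows: 3 days for solicited systemic symptoms, 56 days for all AEs, and for local reactions the post-dose visits shared by the two groups in each pair. Confirm the shared visits from the original schedules; Group 3, for example, has a week 3 visit that Group 6 lacks.
2. Keep the any-dose worst-grade row. Add rows by dose number for Groups 6 and 7, labelled descriptive, with the subjects receiving that dose as denominator. For local reactions use, in Group 6, day of dosing, 72 h and weeks 1, 2, 4 and 8; in Group 7, day of dosing and weeks 1, 2, 4 and 8. Note beside the table that early clinic visits are fewer after doses 2 and 3, which have a 24 h phone contact and a 72 h visit.
3. Define the subgroup as these units.

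The cost is a few table rows and a wording change. Because the rules sit in the protocol, that change needs the sponsor approval and IRB submission described in Section 8.1.

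Separately, as an editorial matter: the visit-window note to Schedule 4 in Appendix III calls Visit 18 not applicable, while Schedule 4 (continued) places it at 72 h on D171 and gives it a +2-day window. These must be reconciled.

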6.4.4 Tolerability Evaluation

The tolerability of the medical product represents the degree to which overt adverse effects can be tolerated by the subject [19]. VRC 605 is the first trial of VRC07-523LS in healthy adults. The tolerability evaluation will be mostly descriptive by nature and consist of solicited AEs that occur during the 3 days following each VRC07-523LS administration and reasons for any withdrawal or discontinuation based upon subject discomfort. This early assessment of tolerability of VRC07-523LS will inform which parameters should be solicited or routinely assessed to further characterize the tolerability profile in a larger number of subjects.

6.4.5 Pharmacokinetics Analysis

Blood samples for PK evaluations will be collected at timepoints per the Schedule of Evaluations.

Individual Subject Pharmacokinetic Analysis: A non-compartmental PK analysis will be performed using Phoenix (Centara) or a similar program on the VRC07-523LS concentration data generated from each subject. Calculated PK parameters for IV Groups 1, 2, 4, 5, and 7 will include: area-under-the-curve (AUC), maximum concentration (Cmax), time to Cmax (Tmax), clearance (CL), volume of distribution (Vdz), terminal elimination rate constant (λz) and the terminal half-life ($T_{1/2}$). For Groups 3 and 6, the PK parameters will include AUC, Cmax, Tmax, apparent clearance (CL/F), apparent volume of distribution (Vdz/F), λz and $T_{1/2}$. Cmax and Tmax will be taken directly from the observed concentration-time data. The terminal slope, λz , will be determined from the log-linear portion of the curve and the $T_{1/2}$ calculated as $0.693/\lambda z$. $AUC_{0-Clast}$ will be determined using the linear trapezoidal method, where C_{last} is the concentration at 12 weeks after the first two doses in Groups 6 and 7 and the concentration at 24 weeks after dose in Groups 1, 2, 4 and 5 and final dose in Groups 6 and 7. If the final sample (C_{last}) has measurable VRC07-523LS concentrations, the remaining AUC after the final concentration ($AUC_{Clast-inf}$) will be estimated as $Clast/\lambda z$. Data will be summarized based by each dose group and overall for IV administration

groups for CL, Vd and $T_{1/2}$. For Groups 6 and 7, potential accumulation will be assessed as the ratios of the $AUC_{0-\infty}$ and C_{max} for the first and the last doses. The potential for non-linearity PKs among IV groups will be determined by comparing the dose-adjusted ratios for C_{max} and AUC between IV groups. Additional compartmental analysis will be performed as warranted by the data.

Population Pharmacokinetic Analyses: Population PK analyses will be performed on the VRC07-523LS PK data following IV and SQ administration to determine compartmental PK parameters with the program NONMEM. One and two compartment PK models will be assessed. Based on prior PK studies of antibodies, including VRC01, it is anticipated that a two compartment model will adequately characterize the data. The population analysis will generate estimates for initial and final volumes of distribution (Vd_1 and Vd_2), inter-compartmental clearance (Q), CL and bioavailability (F). Given the small subject numbers, the population PK analysis will not include an exploratory covariate analysis to assess clinical factors as fixed effects associated with VRC07-523LS PK parameters with the exception of dose (5 vs 20 vs 40 mg/kg), and first vs subsequent doses as a fixed effects on CL, Vd_1 , and Vd_2 . The terminal half-life, $t_{1/2\beta}$ will be determined from CL, Vd_1 , Vd_2 and Q. Final model selection will be based on changes in the objective function and graphically by goodness of fit plots. The final population model will be assessed using bootstrap analysis and dose normalized visual posterior predictive check. VRC07-523LS dosing strategies and their ability to achieve and maintain target VRC07-523LS concentrations will be performed using the final population PK model and Monte Carlo simulations with at least 5000 replicates.

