Research Samples											
Timed PK samples	SST	4	4	4	4	4	4	4	4	4	
⁴ Oral sample						[X]		[X]		[X]	
PBMC and plasma	EDTA			20							
Serum	SST		16	16	16	16	16	16	16	16	
Daily Volume (mL)		15	27	67	20	27	20	20	20	20	
Cumulative Volume (mL)		467	494	561	581	608	628	648	668	688	708

¹ ALT, AST, ALP and creatinine will be collected at all scheduled timepoints. Comprehensive metabolic panel (CMP) will be collected at screening, baseline, and 2 weeks after each product administration and as needed at additional timepoints

² Complete a Reproductive Information Form when pregnancy test is given.

³ HLA type blood sample is collected once at any timepoint in the study and is shown as a Visit 20 evaluation for convenience; however, if HLA type is already available in the medical record it does not need to be repeated. HLA type may also be obtained from a frozen sample.

⁴ Oral mucosa sample collection is encouraged but not mandatory. [X] indicates optional, as needed.

* Subjects who discontinue product administration may be followed weekly for 4 weeks, then monthly for 24 weeks after last injection, per Schedule 3 (continued).

Visit windows: Visit 18 (\pm 6 hrs), Visits 19-22 (\pm 2 days), and Visits 23-27 (\pm 7 days).

Schedule 4: Group 7 (20 mg/kg IV by repeat dosing)																									
Visit Number		01R	02	02A	02B	02C	02D	03	04	06	07	09	10	11	11A	11B	11E	12	13	14	15	16	17	17A	17B
Time After Day 0 Infusion		Pre D0	EOI D0	1hr	3h	6h	24hr	48h	Wk1	Wk2	Wk4	Wk8	Pre Wk12	EOI Wk12	1hr	24hr	72hr	Wk13	Wk14	Wk16	Wk20	Pre Wk24	EOI Wk24	1hr	
^Day of Study		-42 to -1	D0	D0	D0	D0	D0	D1	D2	D7	D14	D28	D56	D84	D84	D84	D85	D87	D91	D98	D112	D140	D168	D168	D168
Clinical	Tube	Screen	Enroll	Day of infusion				Day of infusion				Day of infusion				Day of infusion				Day of infusion					
VRC 500 Screening Consent		X																							
VRC 605 AoU; Consent			X																						
² Screen: Physical exam, ht, wt; Other: targeted exam, BP, pulse, temp; also wt at visits 02, 11, 17		X	X	X	X			X	X	X	X	X	X	X	X		X	X	X	X	X	X	X		
Complete med history at screen; then interim med hx		X	X	X				X	X	X	X	X	X	X			X	X	X	X	X	X	X		
³ VRC07-523LS Administration				X											X									X	
Begin 3-day Diary Card				X											X									X	
Phone contact; clinic visit if indicated																	X								
CBC / diff	EDTA	3		3				3		3	3		3	3						3	3	3		3	3

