⁴ ALT, AST, ALP, creatinine (total bili, BUN, albumin, protein, calcium, Na, K, Cl, CO2, glucose)	GLT	4		4				4		4	4		4	4						4	4	4		4	4
Urine protein		X		X							X			X								X		X	
⁵ Pregnancy test: urine or serum		X	X	X							X			X								X		X	
⁵ Pregnancy prevention counseling/ Reproductive Information Form		X	X	X							X			X								X		X	
HIV EIA (other tests, if needed)	SST	4									4										4				
HIV prevention counseling		X		X						X			X							X				X	
Research Samples																									
Timed PK samples	SST			4	4	4	4	4	4	4	4	4	4	4	4	4	4	4	4	4	4	4	4	4	
⁶ Oral sample (all participants)			[X]												[X]									[X]	
PBMC and plasma	EDTA	20	20																						
Serum	SST	24	24	16						16	16	16	16	16	16	16					16	16	16	16	16
Daily Volume (mL)		55	44	27	4	4	4	4	11	20	31	27	20	27	27	4	4	0	7	31	27	20	27	27	4
Cumulative Volume (mL)		55	99	126	130	134	138	142	153	173	204	231	251	278	305	309	313	313	320	351	378	398	425	452	456

¹ Day 0=day of first product administration. Day 0 is preferably scheduled within 14 days after enrollment, but may be scheduled up to 42 days after enrollment to allow for the possibility of study pauses or scheduling difficulty with the approval of the PI. Day 0 evaluations prior to product administration are the baseline for assessing subsequent AEs.

² Screening includes physical exam with vital signs, height (ht) and weight (wt). At other visits, if medically indicated, a targeted exam is performed. Otherwise only blood pressure (BP), pulse, and temperature are required, except at Visits 02, 11, and 17 when the current weight is also obtained to use for ordering the study product, dosed based on "mg/kg".

³ The PK blood draw "visits," defined by hours after an infusion, are relative to the exact time of the end of infusion. Exact start and end times of product administration and the time of PK blood draw(s) are recorded to ensure accurate PK analysis. All subjects will be observed for 4 hours after each product administration.

⁴ ALT, AST, ALP and creatinine will be collected at all scheduled timepoints. Comprehensive metabolic panel (CMP) will be collected at screening, baseline, and 2 weeks after each product administration and as needed at additional timepoints.

⁵ Pregnancy test results must be negative for women of reproductive potential before each product administration. Complete a Reproductive Information Form when pregnancy test given.

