⁶ Oral mucosa sample collection is encouraged but not mandatory. [X] indicates optional, as needed.

*Subjects who discontinue product administration may be followed weekly for 4 weeks, then monthly for 24 weeks after last administration, per Schedule 4 (continued).

Visit windows: Visits A, B, and C (± 10 min); Visit 02D (-2 hrs); Visit E (+1 day); Visits 03, and 04 (± 6 hrs); Visits 06, 07, 13, and 14 (± 2 days); Visit 12 (+2 days), Visits 09, 10, 11, 15, 16 and 17 (± 7 days, with not less than 21 days between infusions). Visits 05, 08, and 18 are not applicable to Schedule 4.

Schedule 4 (continued): Group 7 (20 mg/kg IV by repeat dosing)												
	Visit Number*	17E	18	19	20	21	22	23	24	25	26	27
	Time After Infusion	24hr	72hr	Wk25	Wk26	Wk27	Wk28	Wk32	Wk36	Wk40	Wk44	Wk48
	Day of Study	D169	D171	D175	D182	D189	D196	D224	D252	D280	D308	D336
Clinical	Tube											
Targeted physical exam, BP, pulse, temp			X	X	X	X	X	X	X	X	X	X
Complete med history at screen; then interim med hx			X	X	X	X	X	X	X	X	X	X
Phone contact; clinic visit if indicated			X									
CBC / diff	EDTA		3	3	3			3	3			
¹ ALT, AST, ALP, creatinine (total bili, BUN, albumin, protein, calcium, Na, K, Cl, CO ₂ , glucose)	GLT		4	4	4			4	4			
Urine protein						X						
Pregnancy test: urine or serum						X			X			X
² Pregnancy prevention counseling / Reproductive Information Form						X			X			X
HIV EIA (other tests, if needed)	SST			4								
HIV prevention counseling					X				X			
³ HLA type	EDTA				20							
Research Samples												
Timed PK samples	SST			4	4	4	4	4	4	4	4	4
⁴ Oral sample							[X]			[X]		[X]
PBMC and plasma	EDTA				20							
Serum	SST			16	16	16	16	16	16	16	16	16
Daily Volume (mL)		0	7	31	67	20	27	27	20	20	20	20
Cumulative Volume (mL)		460	467	498	565	585	612	639	659	679	699	719

¹ ALT, AST, ALP and creatinine will be collected at all scheduled timepoints. Comprehensive metabolic panel (CMP) will be collected at screening, baseline, and 2 weeks after each product administration and as needed at additional timepoints.

² Complete a Reproductive Information Form when pregnancy test is given.

³ HLA type blood sample is collected once at any timepoint in the study and is shown as a Visit 20 evaluation for convenience; however, if HLA type is already available in the medical record, it does not need to be repeated. HLA type may also be obtained from a frozen sample.

⁴ Oral mucosa sample collection is encouraged but not mandatory. [X] indicates optional, as needed.

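### Group 7's observed Cmax is the highest of six early samples after dose 1 but of only two after the last dose, so a last/first accumulation ratio is biased downward by a few percent

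*Combined protocol and SAP*

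**What the plan says.** Section 6.4.5 (Individual Subject Pharmacokinetic Analysis) states that "Cmax and Tmax will be taken directly from the observed concentration-time data". For Groups 6 and 7 it adds that "potential accumulation will be assessed as the ratios of the" AUC to infinity and Cmax for the first and last doses. It does not say which dose is the numerator, and it does not restrict Cmax to sampling times that both doses share.

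Appendix III, Schedule 4, sets the Group 7 sampling times. The Day 0 header runs "EOI D0 1hr 3h 6h 24hr 48h Wk1". The Week 24 dose has only "Pre Wk24 EOI Wk24 1hr" before the table continues to the 24 h and 72 h visits, which carry no PK tube, and then to Week 25. The visit windows read "Visits A, B, and C (± 10 min); Visit 02D (-2 hrs"; no 3 h or 6 h visit exists after doses 2 and 3.

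Section 6.4.5 also plans a population PK model with first versus subsequent doses as a fixed effect. No expected accumulation ratio, assay CV or human half-life for this antibody is stated.

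**The concern.** An antibody concentration falls slowly in the first hours after an infusion. The EOI, 1, 3 and 6 h samples after dose 1 are therefore close to four noisy readings of one peak, and the 24 and 48 h samples can occasionally supply the maximum as well. After the last dose there are two such readings. The highest of several noisy readings tends to exceed the highest of two even if the true peaks are equal, so the first-dose Cmax is inflated relative to the last-dose Cmax. This error is systematic, and more subjects would not remove it.

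The Cmax ratio is one of two named accumulation measures for the repeat-dose IV regimen, and true Cmax accumulation at 12-week dosing is expected to be small. A few percent of downward bias could understate it or bring the ratio to 1 or below. The mechanism is separate from how AUC is calculated, so a change to the AUC method would not correct it.

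**Working it through.** The plan states no accumulation figure to reproduce, so the sample counts were checked first and the bias was then simulated.

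**1. Sample counts from blood volumes (Schedule 4).** Each PK tube is 4 mL. The cumulative row around Day 0 reads "99 126 130 134 138 142 153 173". From the pre-dose total of 126 mL it rises to 130, 134, 138 and 142, which is four 4 mL draws (EOI, 1, 3 and 6 h). It then rises by 11 mL at 24 h (CBC 3 + chemistry 4 + PK 4) and by 20 mL at 48 h (PK 4 + serum 16). For the last dose, the total goes from 452 mL pre-dose to 456 at EOI. The continuation row begins "460 467 498 565 585 612", and its first entry (24 h) carries a daily volume of 0, so the total was already 460 after the 1 h draw. The 72 h visit adds 7 mL (CBC 3 + chemistry 4, no PK). Week 25 adds 31 mL, including the next PK tube. The count is six samples within 48 h after dose 1 and two after the last dose.

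**2. Inputs.**
- From the documents: three doses 84 days apart; five subjects in Group 7; half-life of the related antibody VRC01 given IV, 15.4 days; about 2-fold extension from the LS change (section 1.1); a two-compartment model anticipated (section 6.4.5).
- Assumed: human half-life of 15.4 days (low case) or 15.4 × 2 = 30.8 days; terminal-phase share of the peak f = 0.4 or 0.5; distribution half-life 1 or 3 days; independent lognormal sample error with CV 5 to 20%; ratio expressed as last/first.

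**3. True ratio.** Dose 3/dose 1 = 1 + f(q + q²), where q = 2^(−84/half-life).
- 30.8 days: q = 0.151 and q² = 0.0228, sum 0.174. With f = 0.5 the ratio is 1.087; with f = 0.4 it is 1.070.
- 15.4 days: q = 0.0228 and q² = 0.0005, sum 0.0233. With f = 0.5 the ratio is 1.012; with f = 0.4 it is 1.009.

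**4. Rough size by hand.** For a completely flat peak, the expected maximum of four standard normal readings is 1.029 and of two is 0.564, a gap of 0.465 SD. At CV 10% that is about 0.465 × 0.10 = 0.047 on the log scale, or about 4.5%. Decline over the first hours reduces this gap; the 24 and 48 h samples add a little.

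**5. Simulation of the plan.** Six samples after dose 1 against two after dose 3, with geometric mean ratios, f = 0.5 and distribution half-life 3 days:

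| Half-life | True | CV 5% | CV 10% | CV 15% | CV 20% |
|---|---|---|---|---|---|
| 30.8 d | 1.087 | 1.071 | 1.046 | 1.017 | 0.988 |
| 15.4 d | 1.012 | 0.998 | 0.974 | 0.949 | 0.921 |

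Over the two-compartment shapes tried, at both half-lives, the loss relative to the true ratio is 0.4 to 1.4% at CV 5%, 2.0 to 3.8% at 10%, 4.0 to 6.4% at 15% and 6.1 to 9.1% at 20%. A 40-day half-life moves the upper ends only to 1.5, 3.8, 6.5 and 9.2%. A one-compartment profile (f = 1), which the plan does not expect, gives more: 5 to 6% at CV 10% and 11 to 12% at CV 20%.

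**6. Bias as a share of true accumulation.** At 30.8 days it is 0.27 to 0.44 at CV 10% and 0.76 to 1.05 at CV 20%. At 15.4 days it is about 0.5 to 1.2 at CV 5% and 2.0 to 3.2 at CV 10%.

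**7. Matched times.** Taking the maximum over EOI and 1 h at both doses returns the true ratio within 0.002 in these scenarios. With n = 5 and CV 10%, the SE of the mean log ratio goes from about 0.048 to 0.052.

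**The case against.** A reader might infer that the bias is about as large as the accumulation being sought. The documents do not support that as a general statement. It depends on a CV and a half-life that they do not give, and over the scenarios tried the share runs from under a tenth to several times the accumulation. Section 1.2 describes duplicate serial dilutions averaged within the assay range. This does not fix a CV, but it argues against taking 15 to 20% as typical. Error shared by samples from the same dose would also shrink the effect, so full independence is the unfavourable case.

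A reader might also take downward as unconditional. Section 6.4.5 does not fix the direction, and a first/last ratio would be biased upward.

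The practical stakes are modest. Section 6.3.2 calls the study primarily descriptive, PK is a secondary objective, and no threshold or dosing rule is tied to this ratio. At CV 10% with five subjects, the SE of about 0.05 is at least as large as the bias. Matched times would not prevent chance ratios below 1: with a true ratio of 1.012, about 41% of trials would still show one. The population model does not use an observed maximum, and it is the model used for the dosing simulations. Pre-dose samples at Weeks 12 and 24 show carry-over directly.

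All of this limits the importance of the point. None of it removes the bias from the ratio that section 6.4.5 specifies.

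**Conclusion.** The point holds as a small, correctable bias. The unequal sampling is certain from Schedule 4, and section 6.4.5 has no matched-time rule. Expressed as last/first, the Group 7 Cmax ratio is expected to be too low by about 0.4 to 1.5% at CV 5%, 2 to 4% at 10%, and 4 to 9% at 15 to 20%, assuming independent lognormal error and two-compartment kinetics. If the half-life is near 31 days, this takes roughly 30 to 45% of a true 7 to 9% accumulation at CV 10%, with parity only near CV 20%. If it is near 15 days, the bias usually exceeds the roughly 1% accumulation, which five subjects could not resolve in any case. The population PK analysis is unaffected. This is a worthwhile refinement of one descriptive measure and does not threaten the trial's conclusions.

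**What to change.** In section 6.4.5, add that for the Group 7 accumulation ratio Cmax is the larger of the EOI and 1 h concentrations at each dose, and that the ratio is last/first, reported as the within-subject geometric mean ratio with a 95% CI. Keep the all-sample Cmax for the dose 1 descriptive table.

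The cost is one sentence and a slightly wider interval (SE of the mean log ratio about 0.052 instead of 0.048 at CV 10% with five subjects). No visit, sample or assay changes.
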